6.3.1 Decimal Places

Controlled Quality Management Document		
	Sponsor:	Veru Inc.
	Protocol Number:	V3011902
STATISTICAL ANALYSIS PLAN. PHASE 2-3-4		

Decimal places for derived data described in section 6.2 will be determined by the scale of measurement unless otherwise stated. No decimal places will be displayed if the smallest calculated value is ≥ 100 ; 1 decimal place will be displayed when the smallest value is within the interval (10, 100), with 10 being inclusive; 2 decimal places will be displayed when the smallest value is within (1, 10), with 1 being inclusive; and so on for even smaller scales of measurement.

Derived data where it is known in advance the result will be an integer for example day, month, year, number of days and total scores (for rating scales) will be presented with zero decimal places.

Means, medians and percentiles will be displayed to one more decimal place than the data, dispersion statistics (e.g. standard deviation) will have two more decimal places, and the minimum and maximum will be displayed to the same number of decimal places as reported in the raw data. Percentages will be displayed with one decimal place.

P-values will be quoted to 4 decimal places. P-values < 0.0001 will be presented as $p<0.0001$.

6.4 Subject Disposition

Subject disposition will be summarized as follows:

- The number of enrolled subjects overall in Enrolled Set.
- The number of screen failures overall in Enrolled Set.
- The number of subjects with inclusion/exclusion criteria violations overall in Enrolled Set.
- Number of subjects in each Analysis Set by treatment group and overall in Enrolled Set.
- The reasons for exclusion from the mITT Analysis Set will be summarized by treatment group and overall.
- Study completion, early treatment withdrawal with reason, early study termination with reason and other disposition by treatment group and overall in ITT Analysis Set.

6.5 Protocol Deviations

Protocol deviations will be summarized and listed.

6.6 Baseline Comparability

The comparability of treatment groups with respect to subject demographics and baseline characteristics will be assessed in a descriptive manner, but no formal statistical testing will be performed.

Controlled Quality Management Document		
	Sponsor:	Veru Inc.
	Protocol Number:	V3011902
STATISTICAL ANALYSIS PLAN. PHASE 2-3-4		

Standard continuous or categorical variable summaries will be presented by randomized treatment group for the following variables based on the Safety Analysis Set and mITT Analysis Set:

- Age (years) at Informed Consent
- Age category (<60 years, >=60 years)
- Sex (Female, Male)
- Fertility Status for Women (Childbearing Potential, Post-menopausal, Surgically Sterile)
- Ethnicity (Hispanic or Latino, Not Hispanic or Latino)
- Race (American Indian or Alaska Native, Asian, Black or African American, Native Hawaiian or Other Pacific Islander, White)
- Weight (kg) at Baseline
- Height (cm) at Baseline
- Body Mass Index (BMI) (kg/m²) at Baseline
- WHO Ordinal Scale for Clinical Improvement (descriptive statistics and frequencies for each score category).

The following baseline conditions will be summarized:

- Comorbidities, n (%)
 - Cancer
 - Diabetes
 - Hypertension
 - History of Heart Failure
 - Pneumonia, Renal Issues
 - Respiratory Issues
 - Asthma (subset of Respiratory Issues)
- Oxygen Saturation (SpO₂) (%)
- Creatinine Clearance (mL/min)
- Time from Admission to Randomization (days).

6.7 Medical History

Separate tabulations of previous and ongoing conditions at screening will be presented by randomized treatment group and overall for the Safety Analysis Set.

Controlled Quality Management Document		
	Sponsor:	Veru Inc.
	Protocol Number:	V3011902
STATISTICAL ANALYSIS PLAN. PHASE 2-3-4		

Previous conditions are all conditions which ended before the first dose of study drug.

Ongoing conditions are all conditions which were ongoing at the time of the first dose of study drug.

Conditions will be presented by Medical Dictionary of Regulated Activities (MedDRA, version 24.0) primary system organ class and preferred term.

6.8 Prior and Concomitant Medications

Separate tabulations will be produced for prior and concomitant medications presented by randomized treatment group and overall for the Safety Analysis Set. Prior medications are defined as all medications ending before the date of first dose of study drug. Concomitant medications are defined as medications taken on or after the date of first dose of study drug.

Concomitant medications will be summarized using Anatomic Therapeutic Chemical (ATC) Level 2 and Drug Reference Names using the WHO dictionary (version B3 Mar 2021).

6.9 Exposure to Study Drug

Extent of exposure (number of days of exposure to study drug) will be presented by randomized treatment group for the Safety Analysis Set.

6.10 Treatment Compliance

All subjects will receive standard of care plus oral daily VERU-111 or Placebo. Subjects will take one capsule per day.

Overall study drug compliance (%) will be summarized using descriptive statistics by treatment group and overall. Additionally, compliance (%) will be summarized as frequencies in '<80%', '80-120%' and '>120%' categories.

Overall study drug compliance will be calculated as follows:

$$100 * \frac{\text{number of capsules taken}}{\text{planned total number of capsules}}$$

where planned number of capsules is 1 capsules/day in both VERU-111 and placebo groups. Planned number of capsules will be calculated as last dose date – date of first dose +1.

Controlled Quality Management Document			
	Sponsor:	Veru Inc.	
	Protocol Number:	V3011902	
STATISTICAL ANALYSIS PLAN. PHASE 2-3-4			

6.11 Efficacy Analyses

All statistical tests will be performed using a two-tailed 5% overall significance level, unless otherwise stated. All comparisons between treatments will be reported with 95% confidence intervals for the difference.

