Baseline for WHO Ordinal Scale is the last available record up to and including Day 1. If subject was discharged from the hospital prior to Day 15, 22 or 29 and WHO Ordinal Scale for Clinical Improvement is not collected or record is otherwise missing at those timepoints then the last available observation before or at the time of death/discharge will be carried forward. If subject dies then following time points will be set to the worst possible outcome (score=8).

Controlled Quality Management Document		
	Sponsor:	Veru Inc.
	Protocol Number:	V3011902
STATISTICAL ANALYSIS PLAN. PHASE 2-3-4		

The number and percentage of responders will be summarized by treatment group and visit.

Responders will be analyzed using similar logistic regression model except not planning multiple imputation as the above algorithm provides responder status for all subjects.

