6.11.5.5 Days in hospital

‘Days in hospital’ will be summarized using descriptive statistics (n, mean, standard deviation, median, minimum and maximum) by treatment group.

‘Days in hospital’ will be defined using two different algorithms similarly to ‘Days in ICU’.

‘Days in hospital’ will be analyzed using the same methodology as for ‘Days in ICU’ and the same sensitivity analysis will be performed except the subgroup analyses will not be performed.

6.11.5.6 The proportion of subjects that die on study at Day 15, Day 22, and Day 29.

The number and percentage for all-cause mortality will be summarized by treatment group and visit.

These endpoints will be analyzed using the same methodology as for the primary endpoint (separate analysis will be performed for each visit):

- Multiple imputation + logistic regression model
- Risk differences between treatment groups (using identity link function).

Controlled Quality Management Document			
	Sponsor:	Veru Inc.	
	Protocol Number:	V3011902	
STATISTICAL ANALYSIS PLAN. PHASE 2-3-4			

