6.11.5.1 Change from baseline in viral load (baseline to Day 9)

Descriptive statistics (n, mean, standard deviation, median, minimum and maximum) will be summarized for absolute values and change from baseline by treatment group and visit. For viral load post-BL time points for summary and analysis will be 'Last On-Study' and 'Day 9 only'.

Change from baseline in viral load will be analyzed using the same methodology as for 'Days in ICU' but including also viral load at baseline as covariate.

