6.11.7 Multiplicity

Holm (1979) step-down procedure will be used to control multiplicity for selected key secondary endpoints (days in ICU and days on mechanical ventilation).

If the primary analysis of the primary endpoint is significant at the <0.05 level key secondary endpoints days in ICU and days on mechanical ventilation will be tested using the Holm step-down procedure. In this way an overall type 1 (false-positive) error rate of 5% will be maintained so that no statistical significance for the key secondary efficacy endpoints will be claimed unless the principal analysis of the primary efficacy endpoint using the ITT set is statistically significant at the 5% level.

Holm procedure will be applied as follows:

1. If the p-value for primary endpoint ≥ 0.05 then testing will stop and key secondary endpoints will not be tested. If p-value <0.05 then testing continues to key secondary endpoints.
2. P-values for key secondary endpoints will be sorted from smallest to greatest (ascending order).
3. The smallest p-value for key secondary endpoints will be compared to 0.025.
4. If the smallest p-value yields significant result at 0.025 level then sequential testing continues to the next largest p-value and adjusted alpha value of 0.05. Otherwise the testing will stop.

Data from all analyses, regardless of the level of significance, will be presented for review.

Controlled Quality Management Document	
	Sponsor: Veru Inc.
	Protocol Number: V3011902
STATISTICAL ANALYSIS PLAN. PHASE 2-3-4	

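### Twelve secondary tests, including mortality at Days 15, 22 and 29, run at two-sided 5% with no gate, order or nominal label, so the plan does not limit what may be claimed from them

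*SAP*

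**What the plan says.** SAP 6.11 sets the default for every efficacy test: "All statistical tests will be performed using a two-tailed 5% overall significance level, unless otherwise stated".

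SAP 6.11.7 is the only place that states otherwise for secondary endpoints: "Holm (1979) step-down procedure will be used to control multiplicity for selected key secondary endpoints (days in ICU and days on mechanical ventilation"). The gate there reads: "If the p-value for primary endpoint ≥ 0.05 then testing will stop and key secondary endpoints will not be tested". If the gate opens, "The smallest p-value for key secondary endpoints will be compared to 0.025", and the second p-value is compared with 0.05. The section concludes: "In this way an overall type 1 (false-positive) error rate of 5% will be maintained". The rest of that sentence withholds claims for the key secondary endpoints when the primary endpoint fails. It mentions no other endpoint.

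The remaining secondary endpoints are all formally tested:

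- **Alive without respiratory failure, Days 15, 22 and 29 (SAP 6.11.5.1):** imputation and logistic regression as for the primary endpoint, one analysis per visit.
- **WHO responder, Days 15, 22 and 29 (SAP 6.11.5.3):** "Responders will be analyzed using similar logistic regression model".
- **Days in hospital (SAP 6.11.5.5):** the ICU-days ANCOVA.
- **Mortality, Days 15, 22 and 29 (SAP 6.11.5.6):** "These endpoints will be analyzed using the same methodology as for the primary endpoint (separate analysis will be performed for each visit").
- **Viral load (the section numbered 6.11.5.1 a second time):** "For viral load post-BL time points for summary and analysis will be" the last on-study value and Day 9 alone, by the ICU-days method with baseline viral load added.

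The exploratory section, SAP 6.11.6, holds only a descriptive summary of the WHO-scale area under the curve. Protocol 9.5 has no multiplicity rule for secondary endpoints.

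**The concern.** The gate, the Holm steps and the bar on claims all stop at two endpoints. Every other secondary test falls back on the 6.11 default of two-sided 5%, whether or not the primary endpoint succeeds.

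Early mortality is the most sensitive case. It repeats the primary comparison, with the same model, at three earlier days. If Day 60 mortality misses its criterion, nothing in the SAP prevents Day 15, 22 or 29 mortality from being reported as significant at 5%. If Day 60 mortality succeeds, the error control stated in 6.11.7 covers three tests: the primary and the Holm pair. The status of the others is still undeclared. What is at stake is the set of statements the study report may make from secondary results, not the primary test.

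**Working it through.** **1. The plan's own figure.** Holm for two endpoints uses 0.025 and then 0.05, so the bound is 2 × 0.025 = 0.05. Simulation under no effect gives 4.96% at correlation 0, 4.65% at 0.5 and 4.02% at 0.8. The 5% for the pair reproduces, and tests outside the family do not change it.

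**2. Count of tests outside the pair** (SAP 6.11.5; subgroups, sensitivity analyses and identity-link repeats left out):

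| Endpoint | Tests |
|---|---|
| Alive without respiratory failure, Days 15, 22, 29 | 3 |
| WHO responder, Days 15, 22, 29 | 3 |
| Mortality, Days 15, 22, 29 | 3 |
| Days in hospital | 1 |
| Viral load, two time points | 2 |
| **Total** | **12** |

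The total is 11 if Day 29 alive without respiratory failure is set aside because its status is disputed (see the fix).

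**3. Chance of at least one p<0.05 with no true effect.** If independent, it is 1 − 0.95^11 = 0.431 for 11 tests and 1 − 0.95^12 = 0.460 for 12. The endpoints are in fact correlated. The documents give no correlation, so a common value is assumed and normal test statistics are simulated with rejection at |z| > 1.96:

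| Assumed correlation | 11 tests, any p<0.05 | 11 tests, any favouring VERU-111 | 12 tests, any p<0.05 |
|---|---|---|---|
| 0 | 43% | 24% | 46% |
| 0.2 | 40% | 21% | 43% |
| 0.5 | 30% | 15% | 32% |
| 0.8 | 18% | 9% | 19% |

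Two other structures fall within this range. Correlations of 0.6-0.9 within an endpoint family and 0-0.6 between families give 22-38%. An illustrative patient-level null simulation (140:70, unadjusted z-tests, all three respiratory-failure days and one viral load test) gives 25-29%, with about 12-15% favouring VERU-111.

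**4. Early mortality alone.** The documents do not give the timing of deaths. Assume that 30-60%, 50-80% and 65-90% of Day 60 deaths have occurred by Days 15, 22 and 29. With independent increments, the correlation of an early test with the Day 60 test is the square root of that fraction: √0.30 = 0.55 to √0.60 = 0.77 at Day 15, and √0.65 = 0.81 to √0.90 = 0.95 at Day 29. Under no effect:

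- At least one early day reaches p<0.05 in 8.6-9.9% of trials.
- At least one early day does so while Day 60 misses 0.0452 (the final criterion in Protocol 9.7.2) in 5.0-7.4%.
- Half of that is 2.5-3.7% in favour of VERU-111; direct simulation gives 2.4-4.0%.

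A patient-level check with 18% mortality assumed in both arms gives 8.6-9.5% and 5.0-7.2% for the first two figures.

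**The case against.** The strongest reply is that the SAP never promises 5% across these tests. SAP 6.11.7 ties its 5% to the primary endpoint and two selected secondary endpoints, and that control holds. A reader might infer from 6.11 that the whole set of secondary tests is meant to share one 5% error rate and that the plan breaks this promise. The documents do not support that: the word overall in 6.11 is ambiguous and can be read as a default level for each test. This part of the reply stands.

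It can also be said that no claim from these tests is planned, and that 6.11.7 merely presents all results for review. It is true that no passage announces such a claim. But presenting results is not the same as limiting claims, and 6.11 gives each test a significance level. An explicit default together with an explicitly narrow exception is more than silence.

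Third, the size is modest. The rates are two-sided and depend on assumed correlation and death timing, and only about 2.5-4% of null trials would show a favourable early mortality result alongside a failed Day 60. This stands, and no single percentage should be quoted as the error rate. Nor should a reader infer that an early mortality result could replace the primary endpoint, since both documents name Day 60 mortality as the only primary.

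Finally, the viral load endpoint is already defined as baseline to Day 9. That is so, but the SAP also sends the last on-study value to analysis without saying which result answers the endpoint.

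**Conclusion.** The point holds as a gap in claim control. Twelve secondary tests (11 without Day 29 respiratory failure) have a two-sided 5% level but no gate, order or nominal status, and the bar on claims after a failed primary does not reach them. For 11 tests under no effect, the chance of at least one p<0.05 is about 18-40% at assumed correlations of 0.8 to 0.2, and 43% if independent; roughly half of these favour VERU-111. An early mortality test is significant while Day 60 fails in about 5-7% of null trials, or about 2.5-4% in favour of VERU-111, under assumed death timing.

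These tests do not harm the primary analysis or the Holm pair. A primary gate alone would not be enough: if the primary effect is real the gate opens, and the other tests remain unadjusted. Whether the gate itself should be 0.05 (SAP 6.11.7) or 0.0452 (Protocol 9.7.2) is a separate matter.

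**What to change.** First reconcile which secondary endpoints are key. Protocol 4.2 and 5.3.2 and SAP 2.2 and 3.2 give that status to alive without respiratory failure at Day 29; SAP 6.11.7 gives it to ICU days and ventilator days. Day 29 should not become nominal by default through the new wording.

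Then add to SAP 6.11.7:

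> Statistical significance will be claimed only for the primary endpoint and, if its criterion is met, for the key secondary endpoints in the controlled family. All other secondary endpoints and time points, including mortality at Days 15, 22 and 29, will be reported with estimates, 95% confidence intervals and p-values labelled nominal, whatever the primary result.

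Narrow the sentence in SAP 6.11 to match. In the viral load section, name Day 9 as the analysis of the stated endpoint and the last on-study value as supportive. Label the pre-Day 60 results in Table 14.2.1.2 as nominal; only the table's title is available, so the layout is for the sponsor to settle.

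The cost is SAP wording and table labels, with no new data or patients. The downside is that the sponsor gives up significance language for these endpoints.

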6.11.1 Primary Efficacy Analysis

The primary endpoint for the study will be the proportion of subjects that die on study (up to Day 60). Responders are subjects who are alive at Day 60.

The number and percentage of deaths will be summarized by treatment group.

Mortality rates will be analyzed using a logistic regression model. The model will include treatment as a factor and gender, study site (or country or region), remdesivir use (No/Yes), dexamethasone use (No/Yes) and WHO Ordinal Scale strata used in randomization as covariates. The model will be fitted using logit link function. Odds ratios, standard errors, 95% confidence intervals and p-values for the treatment difference will be presented.

The primary analysis will be performed on the ITT analysis set and the ITT data scope regardless of patient's use of rescue medications, protocol violations or investigational product discontinuation consistent with the treatment policy strategy. Every effort will be made to collect vital status up to the end of the study period. Missing data for subjects who are lost to follow up will be imputed using multiple imputation methods.

Example SAS code for imputation is as follows:

```
proc mi data=xxx out=imputed1 seed=1234 n impute=50;
class treatment sex site discharge discont remdesivir dexamethasone whostrata
imputedresponse;
fcs logistic(imputedresponse / details likelihood=augment);
var treatment sex site discharge discont remdesivir dexamethasone whostrata
imputedresponse;
run;
```

where IMPUTEDRESPONSE is the response variable to be imputed, TREATMENT is the randomized treatment group (veru/placebo), SEX is sex of the subject (male/female), SITE is study site (if there are issues fitting imputation model then this might be replaced with country or region), DISCHARGE is whether the subject was discharged from the hospital at any time during the study

Controlled Quality Management Document	
	Sponsor: Veru Inc.
	Protocol Number: V3011902
STATISTICAL ANALYSIS PLAN. PHASE 2-3-4	

(no/yes, populated as ‘no’ for subjects who were not discharged from the hospital prior to withdrawing from the study before Day 60), DISCONT is whether subject discontinued treatment early (no/yes), REMDESIVIR is the use of remdesivir at baseline (no/yes), DEXAMETHASONE is the use of dexamethasone at baseline (no/yes) and WHOSTRATA is the WHO Ordinal Scale strata used in randomization. If the imputation model does not converge when both DISCHARGE and DISCONT variables are included then will be checked if either of them alone can be included in the model. If model converges with DISCHARGE or DISCONT alone but the model with both DISCHARGE and DISCONT does not converge, then imputation model will include only DISCHARGE.

The imputed data sets will be analyzed separately for each imputation using the logistic regression model. If all subjects have the mortality status at Day 60 then the imputation part above will not be used and observed data will be analyzed as such. Example SAS code for logistic regression is as follows:

```
proc logistic data=imputed1 order=internal descending;
by _imputation_;
class imputedresponse treatment sex site remdesivir dexamethasone whostrata
  / param=glm;
model imputedresponse = treatment sex site remdesivir dexamethasone whostrata
  / clodds=both firth;
estimate 'Treatment A vs. Treatment B' treatment 1 -1 / cl e exp;
lsmeans treatment / cl exp diff;
ods output modelanova=imputed_modelanova1
  lsmeans=imputed_lsmeans1
  diffs=imputed_diffs1
  parameterestimates=imputed_parmest1;
run;
```

If there are enough deaths to perform analysis without FIRTH option then it might be dropped out. Note that variable _IMPUTATION_ identifies each of the imputations created by PROC MI.

Finally, results from individual imputations are pooled via Rubin’s rules using PROC MIANALYZE. Example SAS code for pooling log(odds) for each treatment group is as follows:

```
proc mianalyze data=imputed_lsmeans1;
by trt01pn;
modeleffects estimate;
stderr stderr;
ods output parameterestimates=combined_odds1;
```

run;

Example SAS code for pooling log(odds ratio) for each treatment group is as follows:

```
proc mianalyze data=imputed_diffs1;
  modeleffects estimate;
  stderr stderr;
  ods output parameterestimates=combined_diffs1;
run;
```

